10.16. Appendix 16: Protocol Amendment History

The Protocol Amendment Summary of Changes Table for the current amendment is located directly before the Table of Contents (TOC).

Amendment [a]

Overall Rationale for the Amendment:

The purpose of this amendment is to clarify the surveillance colonoscopy requirements and to update protocol wording to align with current regulatory requirements.

Minor editorial changes are not included in this table.

Section # and Name	Description of Change	Brief Rationale
1.3. Schedule of Activities	Removed the 'X' indicator for	To align with the analysis strategy.
	at ED visit.	
5.1. Inclusion Criteria	Criterion 6: Added specific	To clarify the surveillance colonoscopy
	surveillance colonoscopy criteria	requirements.
	to clarify the requirements for	
	eligibility prior to Visit 2.	
6. Study Intervention(s) and	Reworded the definition of study	To improve alignment with regulatory
Concomitant Therapy	intervention.	definitions.
8.1.5.2. Surveillance	Added specific surveillance	To maintain consistency with revisions
Colonoscopy Requirements	colonoscopy criteria to clarify	in Section 5.1, and to allow for regional
	the requirements for eligibility	differences in biopsy requirements for
	prior to Visit 2; and removed	surveillance colonoscopies in
	subsection on minimum	participants with moderately to severely
	colonoscopy biopsy procedural	active UC.
	requirements.	
10.1.4. Data Protection	Added statements to clarify	To address an EU CTR (536/2014)
	methods for protection of	requirement.
	personal data and handling of	
	data security breach.	
10.3.6. Regulatory Reporting	Added a description of the	To address an EU CTR (536/2014)
Requirements	reporting of SUSARs.	requirement.
10.12.1. Overview (of	Clarified that the Continued	To maintain consistency with statement
Appendix 12: Optional	Access Period may be stopped if	in Section 10.12.7.
Continued Access Period)	sponsor discontinues plans for	
	seeking regulatory approval "in	
	any markets" rather than "within	
	the participant's country."	
10.12.3. Schedule of Activities	Removed the footnote indicator	To correct a typographical error.
for Continued Access Period	on HBV DNA cell for Visit 501.	
10.12.5.1. Inclusion Criteria (of	Revised Criterion 55.	To maintain consistency with other
Appendix 12: Optional		sections of the protocol.
Continued Access Period)		

11. References

ATC	anatomical therapeutic chemical	
AZA	azathioprine	
BMI	body mass index	
BOCF	baseline observation carried forward	
CCI		
CAP	continued access period	
CFB	change from baseline	
CI	confidence intervals	
CMI	clinically meaningful improvement	
CCI		
CSR	Clinical Study Report	
ECG	electrocardiogram	
eCRF	Electronic case report form; an electronic document designed to record all the protocol-required information to be reported to the sponsor for each trial participant	
EIM	extraintestinal manifestation	
ES	endoscopic subscore	
FAS	Full Analysis Set	

Term	Definition	
CCI		
HLT	High Level Terms	
IBD	Inflammatory Bowel Disease	
CCI		
ICH	International Council for Harmonisation	
informed consent	A process by which a participant voluntarily confirms their willingness to participate in a particular study, after having been informed of all aspects of the study that are relevant to the participant's decision to participate. Informed consent is documented by means of a written, signed, and dated informed consent form	
interim analysis	An interim analysis is an analysis of clinical study data, separated into treatment groups, that is conducted before the final reporting database is created or locked	
investigational product	A pharmaceutical form of an active ingredient or placebo being tested or used as a reference in a clinical trial, including products already on the market when used or assembled (formulated or packaged) in a way different from the authorized form, or marketed products used for an unauthorized indication, or marketed products used to gain further information about the authorized form.	
ISR	Infusion/Injection Site Reactions	
IV	intravenous	
JAK	Janus Kinase	
LLT	Lowest Level Term	
MACE	major adverse cardiovascular events	
MedDRA	Medical Dictionary for Regulatory Activities	
MI	multiple imputation	
MMS	Modified Mayo Score	
MMX	multi matrix colonic delivery technology	
NAb	neutralizing anti-drug	
NRI	nonresponder imputation	
NRS	numeric rating scale	
OI	opportunistic infections	

Term	Definition	
OR	odds ratio	
Participant	Equivalent to CDISC term "subject": an individual who participates in a clinical trial, either as recipient of an investigational medicinal product or as a control	
PD	Pharmacodynamics	
PGA	Physician's Global Assessment	
CCI		
	у	
PK	pharmacokinetics	
PT	preferred term	
Q4W	once every 4 weeks	
CCI		
QoL	quality of life	
RB	rectal bleeding	
CCI		
S1P	Sphingosine-1-phosphate	
CCI		
SAE	serious adverse event	
SAP	statistical analysis plan	
SC	subcutaneous	
Screen	The act of determining if an individual meets minimum requirements to become part of a pool of potential candidates for participation in a clinical study	
CCI		
SF	stool frequency	
SMD	standardized mean difference	
SMQ	standardized MedDRA query	
SoA	Schedule of Activities	
SOC	system organ class	
ТВ	tuberculosis	

CONFIDENTIAL

Term	Definition
TBL	total bilirubin level
TEAE	Treatment-emergent adverse event: An untoward medical occurrence that emerges during a defined treatment period, having been absent pretreatment, or worsens relative to the pretreatment state, and does not necessarily have to have a causal relationship with this treatment
TNF	tumor necrosis factor
UC	ulcerative colitis
ULN	upper limit of normal
UNRS	urgency numeric rating scale
CCI	

Version history

This Statistical Analysis Plan (SAP) for study I6T-MC-AMBZ is based on the protocol dated 16FEB2023.

 Table AMBZ.1.0.
 SAP Version History Summary

SAP Version	Approval Date	Change	Rationale
1.0	05APR2023	Not Applicable	Original version
2.0	24APR2024	No Changes	Version updated to reflect yearly review
3.0	21NOV2024	Section 1.2	Added details about the continued access period and continued access follow-up period start and stop details
		Table AMBZ.4.1.	Updated language for period definition to accommodate Continued Access Period.
		Section 4.3.2 Main analytical approach	Added explanation for odds ratio, Youden's index and standardized mean difference methods.
		Table AMBZ4.2	Switched binary and continuous variables in the ANCOVA analysis
		Table AMBZ4.3	Added footnotes to describe confidence interval analysis
		Table AMBZ.4.3 Table AMBZ.6.2.	Updated APU for bowel urgency from bowel urgency measures to QoL measures, adjusted table for APU correlation analysis accordingly.
		4.6.2 Adverse Events	Added additional explanation for TEAE definition. Updated language that some safety analysis listings may be provided as appropriate.
		4.6.7 Concomitant Therapy/ Procedure	Updated procedures from 'will be summarized' to 'may be summarized.'
		Section 4.5.1	Added CCI to analysis.
		Table AMBZ.6.1.	Updated language for description and definition of
		Table AMBZ.6.3	Removed CCI from options on the prior therapy eCRF for biologic agents in footnote.

CONFIDENTIAL

		Updated definition of location of disease
		Added a footnote for definition of S1P.
		Added prior advanced therapy exposure and prior advanced and biologic therapy failure.
		Updated prior therapy exposure and failure
	Table AMBZ.6.4.	Updated language for daily diary time window calculation.

1.

Introduction

This document describes the rules and conventions to be used in presenting and analyzing the efficacy and safety data for the AMBZ study. It describes the data and details statistical analyses that will be performed.

[figure not shown]
There are no changes to the analyses described in the protocol.

[figure not shown]
1.1. Objectives, Endpoints, and Estimands

[figure not shown]
Table AMBZ.1.1 shows the protocol-defined primary, secondary and exploratory objectives and endpoints of the study. The estimands (ICH E9R1 2017) associated with primary and secondary endpoint/analysis are also described in this section.

Table AMBZ.1.1. Study objectives and endpoints

Objectives	Endpoints
Primary	
• To assess the improvement in bowel urgency severity at Week 12.	Change from baseline in bowel urgency severity (UNRS) score at Week 12.
Secondary	
 To assess the improvement in bowel urgency severity at Week . To assess the improvement in . 	
• To assess the improvement in CCI	
• To assess the proportion of participants achieving clinical remission and a UNRS score	

Abbreviations: QoL = quality of life; UC = ulcerative colitis; UNRS = urgency numeric rating scale.

1.2. Study Design

This is a multicenter, open-label, single-arm Phase 3b study to investigate bowel urgency and its relationship with other outcome measures in participants with moderately to severely active UC treated with mirikizumab over a colored week period.

Design

The study will have 4 study periods:

Period I (days)

Participants must complete all Visit 1 screening activities within days prior to Visit 2. The screening endoscopy must occur within days prior to Visit 2.

Period II (weeks)
Participants will receive CCI mg mirikizumab CCI
Period III (weeks)
Participants will receive CCI mg mirikizumab CCI

Note: Participants planning to participate in continued access must complete self-administration training during at least 2 visits between Visits 6 and 9 (see Section 6.1.1 of protocol). Upon completion of all Visit 10 activities, eligible participants may enter the Continued Access Period.

Period IV

Participants who meet the following criteria should enter posttreatment follow-up, including completion of Visit 801:

Continued Access Period (CAP)

Participants who successfully completed Visit 10 and are eligible to enter the CAP. Participants will enter the CAP on the same day that they complete Visit 10 and remain until they discontinue from treatment in the CAP portion of the study. The CAP period will begin at dose of Visit 501 minus 1 minute and end at treatment discontinuation visit.

Continued Access Follow-up Period

Participants who entered the CAP and then discontinued treatment will enter the CAP follow-up period. They exit the CAP follow-up period when they complete Visit 901.

See Figure AMBZ.1 in this SAP for schema. The Schedule of Activities (SoA) is described in Section 1.3 of protocol.

CCI

^a Participants who are eligible for continued access should move directly from Visit 10 to Visit 501, on the same day, if possible. Visit 801 should not be performed.

b Optional Continued Access Period is described in Section 10.12 of the protocol.

2. Statistical Hypotheses

The primary objective is to assess the improvement from baseline in UNRS in participants treated with mirikizumab at Week. No formal hypothesis testing will be performed on the primary endpoint.

2.1. Multiplicity Adjustment

Multiplicity control is not applicable for this study.

3. Analysis Sets

Analysis sets are defined in Table AMBZ.3.1 along with the planned analysis for each set. For both analysis sets, participants will be analyzed according to their assigned treatment unless otherwise specified.

Table AMBZ.3.1. Analysis sets

Population	Description		
Full Analysis	Definition: All participants who are assigned to treatment and receive at least 1		
Set (FAS)	(partial or complete) dose of study treatment (regardless of whether the participant		
	does not receive the correct treatment, or otherwise does not follow the protocol).		
	Purpose: Used for efficacy and health outcomes analysis		
Safety Analysis	Definition: All participants who are assigned to treatment and receive at least 1		
Set	(partial or complete) dose of study treatment (regardless of whether the participant		
	does not receive the correct treatment, or otherwise does not follow the protocol).		
	Purpose: Used for safety-related analysis		

4. Statistical Analyses

4.1. General Considerations

Statistical analysis of this study will be the responsibility of Eli Lilly and Company (hereafter Lilly) or its designee. The statistical analyses will be performed using SAS® Version 9.4 or higher. The version of the Medical Dictionary for Regulatory Activities (MedDRA®) will be 24.0 or higher.

Any change to the data analysis methods in the protocol will require an amendment only if it changes a principal feature of the protocol. Additional exploratory analyses of the data will be conducted as deemed appropriate. Not all displays and analyses described in this SAP will necessarily be included in the clinical study report (CSR). Not all displays will necessarily be created as a "static" display. Some displays may be incorporated as interactive display tools instead of or in addition to a static display.

4.1.1. Analysis Methods

When reported, descriptive statistics will include the number of participants; mean, standard deviation, median, minimum, first and third quartile, and maximum for continuous measures; frequency counts and percentages for categorical measures; and estimate and 95% confidence intervals (CI) for correlation coefficients.

4.1.2. Definition of Baseline

For efficacy and health outcomes analysis, baseline refers to the values or observations collected prior to or on the day of the initiation of study treatment in Study AMBZ, unless otherwise specified.

The baseline for variables collected as part of the daily diary (including the patient-reported outcomes components of the Modified Mayo Score, stool frequency (SF) and rectal bleeding (RB) subscores) will be calculated from valid daily diary entries obtained prior to baseline endoscopy preparation (see Appendix 6). The baseline endoscopy component of the Mayo Score will use the endoscopic appearance of the mucosa at the AMBZ screening endoscopy. For other efficacy and health outcome assessments, baseline is defined as the last non-missing assessment recorded on or prior to the date of the first study drug administration at Visit 2 (Week 0) in Study AMBZ.

Baseline for safety analysis is described in the Section 4.6.2 and Section 4.6.3.

Change from baseline will be calculated as the visit value of interest minus the baseline value. If a baseline value or the value at the visit is missing for a particular variable, then the change from baseline is defined as missing.

4.1.3. Definition of Study Period Time Interval

Table AMBZ.4.1 displays a list of study periods along with the definition of which participants will be considered to have entered the study period and when the individuals start and end the study period (refer to Appendix 6 for additional details on study visits and study weeks). See Section 10.12 of protocol for more details about Continued Access Period (CAP).

To calculate the length of any time interval or time period in this study the following formula will be used:

 $Length\ of\ interval\ (days) = End\ Date\ -\ Interval\ Start\ Date\ +\ 1$

To convert any time length from days to years, the following formula will be used:

Length of interval (years) = Length of interval (days)/365.25

To convert any time length from days to weeks, the following formula will be used:

Length of interval (weeks) = Length of interval (days) /7

Only for the purpose of calculating the length of study period time intervals, the words "prior to" in Table AMBZ.4.1 should be understood to mean "the day/time before" while the words "after" should be understood to mean "the day/time after." For the purpose of determining whether a date/time lies within an interval, these words are intended to convey whether the start or end of the period is inclusive of the specified date.

Table AMBZ.4.1. Definition of Main Study Period Time Intervals (excluding Continued Access Period)

Main Study Period	Interval Start Definition	Interval End Definition	
Period I (Screening):	Informed consent date	Prior to the start of study	
All participants who sign		treatment.	
informed consent are considered			
as entering the Screening Period.			
Period II (CCI mg mirikizumab	At the date/time of first	Prior to first administration of	
cci):	administration of CCI mg	cci mg mirikizumab cci, or	
All participants who received any	mirikizumab 🚾	discontinuation of study	
amount of mirikizumab are		treatment, whichever is earlier	
considered as entering Period II			
and the treatment period.			
Period III (CCI mg	At the date/time of first	Week Visit, or	
mirikizumab COI):	administration of CCI mg	discontinuation of study	
All participants who received any	mirikizumab CCI	treatment, whichever is earlier	
amount of mirikizumab on are			
considered as entering Period III.			
Period IV (Follow up)	After last date of any study	The maximum of the last	
All participants who discontinued	treatment period for patients	study visit and study	
mirikizumab treatment prior to	who did not enter CAP.	disposition date for patients	
Visit 10, or completed Visit 10		who did not enter CAP.	
and who did not enter CAP are			
considered to have entered the			
follow-up period.			

Abbreviations: CCI CAP = continued access period.

[figure not shown]
The CCI

The coweek analysis will include analysis through Week (Period III) but will not include analysis during the CAP. All safety and efficacy data will be included unless otherwise specified.

The CAP analysis will include a basic safety analysis, including disposition, analysis of AEs, vital signs, and lab data. Additional analysis during CAP will be performed as appropriate. All data from screening to end of CAP will be generally included.

4.1.4. Missing Data Imputation

CCI

4.1.5. Protocol Deviations

Protocol deviations will be identified throughout the study. The protocol deviation categories will be described per Protocol Deviation Management Plan and Trial Issues Management Plan by clinical team. Important protocol deviations are defined in Protocol Deviation Management Plan as those deviations from the protocol that may significantly impact the completeness, accuracy and/or reliability of study data or that may significantly affect a subject's rights, safety or well-being.

4.2. Participant Dispositions, Baseline Characteristics and Medical History

The treatment disposition and study disposition will be summarized for the FAS population. The reason for discontinuation from treatment and from study will be included.

All FAS participants who discontinued from the study and/or study treatment during any period of the study will be listed with the reported study treatment discontinuation and study discontinuation times. If known, a reason for their discontinuation will be given.

4.2.1. Demographics and Baseline Characteristics

Summaries and listings of the demographic and baseline characteristics detailed in Appendix 3 will be presented.

4.2.2. Non-UC Medical History

Non-UC medical history will be collected on the Pre-Existing Conditions and Medical History case report form (CRF) and coded using MedDRA version 24.0 or higher. The version used to code medical history will be displayed in the outputs. All medical history will be summarized for the Safety Set by system organ class and preferred term. Prespecified medical history of liver and concurrent disease, hypersensitivity event, and associated person medical history of liver disease collected on the respective CRFs will also be summarized.

4.3. Primary Endpoint Analysis

4.3.1. **Definition of Endpoint(s)**

The primary endpoint is defined in Table AMBZ.1.1, description and derivation of endpoints are described in Table AMBZ.6.1.

4.3.2. Main Analytical Approach

Analysis of the primary endpoint is described in Table AMBZ.6.2.

continuous measure for each participant as the average daily diary score over a day period. The difference between the UNRS score at Week and at baseline will be calculated for each participan
and averaged. CCI
CCI

4.4. Secondary Endpoints Analysis

Section 4.1.4.

4.4.1. **Definition of Endpoint(s)**

The secondary endpoint is defined in Table AMBZ.1.1 Derivation details are described in Table AMBZ.6.1.

4.4.2. Main Analytical Approach

The analysis of the secondary endpoints is described in Table AMBZ.6.2. Descriptive summaries and CI will be provided for continuous and binary secondary endpoints as indicated in Section 4.1.1.

Analysis of association between secondary endpoints is described in Table AMBZ.4.2 and Table AMBZ.4.3. At Week or Week these analyses will be performed among participants with available data that do not discontinue prior to the time point of interest.

Table AMBZ.4.2. Type of Endpoints and Association Analyses

[figure not shown]
Dependent Outcome	Explanatory Outcome	Analysis
Continuous	Continuous	
Continuous	Binary	UUI
Binary	Binary	

Abbreviations: COl Youden's index (Youden 1950) (Kadel 2012); YI =

Table AMBZ.4.3. Type of Assessments and Endpoints for Association Analyses

Assessments	Endpoint Type	Endpoint	
Bowel Urgency	Continuous	UNRS, BUF, SDT, CCI	
Assessments			
	Binary	UNRS CMI, UNRS Remission	
QoL/Function Measures	Continuous	CCI	
	Binary	CCI	
Symptom/ Symptom Severity of UC	Continuous	CCI	
	Binary	CCI	
Histological Features	Continuous	(Analysis value, and CFB if applicable)	

Assessments	Endpoint Type	Endpoint
	Binary	
Additional Exploratory Measures	Continuous	

The odds ratio (OR) is calculated using logistic regression with 95% Wald confidence intervals, as implemented in SAS PROC LOGISTIC.

The Youden's Index (YI) and corresponding 95% confidence intervals are calculated using the equations presented in Youden, W.J. (1950).

The standardized mean difference (SMD) is calculated by mean difference divided by pooled standard deviation, where pooled standard deviation is obtained by taking the square root of the weighted average of the variances of each group in binary outcome, where the weights are the degrees of freedom of each group.

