1.3. Schedule of Activities (SoA)

Period I

Completion of the Visit 1 screening activities requires more than 1 day.

Period II

Visit 3 is a telephone visit. All safety assessments should be performed by telephone.

Period III

Upon completion of all Visit 10 activities, eligible participants may enter the Continued Access Period. These participants will move directly from Visit 10 to Visit 501 of the Continued Access Period if they meet requirements detailed in Section 10.12.

Period IV

Visit 801, a telephone visit, should be performed CCI days after the participant's last visit, either Visit 10 or the ED visit.

Visit 801 may be performed onsite when onsite activities are required or at investigator's discretion.

Early discontinuation (ED) visit

Required for all participants who discontinue mirikizumab treatment prior to Visit 10.

Unscheduled visits (UV)

May occur as needed, on any day without regard to visit interval. Required activities are indicated in the SoA. Additional procedures may be performed at the investigator's discretion.

	I		II	I		III						IV	Comments	
Visit number	1	2	3	4	5	6	7	8	9	10	ED	UV	801	Dosing visits: complete all visit activities before administration of mirikizumab.
Weeks from treatment assignment														
Study day														
Visit interval														
tolerance (days)														
Visit location	О	О	T	О	О	О	О	О	O	0	0	О	T	O = Onsite, T = Telephone
Informed consent	X													The informed consent form (ICF) must be signed before any protocol-specific activities are performed. See Section 10.1.3.
Inclusion and exclusion	X	X												Confirm before Visit 2 assignment
criteria, review and														and administration of first dose.
confirm eligibility														
Demographics	X													Includes year of birth, sex, race, and ethnicity (where permissible).
Preexisting conditions	X													Collect all ongoing conditions;
and medical history														relevant surgical or medical history.
Prespecified medical	X													Collect additional data for UC and
history (UC and history														comorbidities of interest.
of interest)														
Prior treatments for UC	X													
Substance use	X					X				X	X		X	
including alcohol, caffeine, tobacco,														
nicotine														
Concomitant	X	X	X	X	X	X	X	X	X	X	X	X	X	
medications	21	2.	2.	21	2.	11	2.1	1.	11	71	21	2.5	11	Refer to Section 6.8.
Adverse events (AEs)	X	X	X	X	X	X	X	X	X	X	X	X	X	See Sections 8.3.1 and 8.3.3.

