	I		I	I		III							IV	Comments
Visit number	1	2	3	4	5	6	7	8	9	10	ED	UV	801	Dosing visits: complete all visit activities before administration of mirikizumab.
Weeks from treatment assignment														
Study day														
Visit interval tolerance (days)														
Visit location	0	0	T	0	О	0	0	0	О	0	0	0	Т	O = Onsite, T = Telephone
Pre-endoscopy instructions and reminders	X				X				X					Includes diary compliance, dates, and bowel preparation/procedure
Physical Evaluation				l			l			l	. 			
Height	X													
Weight	X	X				X				X	Х			
Vital signs	X	X		X	X	X	X	X	X	X	X	X	Χŧ	† optional per investigator discretion. See Section 8.2.2.
Physical examination	X													See Section 8.2.1.
Symptom-directed physical assessment		X		May	perfor		y visit,	per inv	estigator	X	X	X	Xŧ	† optional per investigator discretion. See Section 8.2.1.
Evaluate for EIMs	X	X		Mayı	perfor		y visit,	per inv	estigator	X	X			See Section 8.2.1.
Tuberculosis (TB) evaluation		X				X		X		X	X			Risk factors and symptoms of active TB. See Section 8.2.7.
Chest X-ray	X													For instructions and exceptions, see Section 8.2.7.1.
12-lead ECG (local)	X													See Section 8.2.3.
Participant Diary (Elec	etronic)													
Diary dispensed	X													Explain use of device and each measure. See Section 8.1.1.

	I		П	[III					IV	Comments
Visit number	1	2	3	4	5	6	7	8	9	10	ED	UV	801	Dosing visits: complete all visit activities before administration of mirikizumab.
Weeks from treatment assignment														
Study day														
Visit interval tolerance (days)														
Visit location	0	О	T	О	О	О	О	О	О	0	0	О	T	O = Onsite, T = Telephone
Diary compliance check, retraining as needed	X.	X	X	X	X	Xļ	X	X	X	Χļ	X			X↓: Site personnel must ensure diary completed on 4 or more (≥4) of 7 days prior to bowel preparation at V1, V6, and V10. See Section 8.1.1.
Diary returned										X	X			
Patient-Reported Outco	mes (Elec	tronic	tablet)											
CCI	X													CCI
CCI				X	X	X				X	X			
CCI		X				X		X		X	X			
CCI		X				X		X		X	X			

	I		n	[Ш					IV	Comments
Visit number	1	2	3	4	5	6	7	8	9	10	ED	UV	801	Dosing visits: complete all visit activities before administration of mirikizumab.
Weeks from treatment assignment														
Study day														
Visit interval tolerance (days)														
Visit location	О	О	Т	О	О	О	О	О	О	0	0	О	T	O = Onsite, T = Telephone
		X				X		X		X	X			
UUI		X				X				X	X			
		X				X				X	X			
		X				X				X	X			
		X				X				X	X			

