4.5. Exploratory Endpoints Analysis

Analysis of the exploratory endpoints other than gene expression endpoints are described in Table AMBZ.6.2. Analysis of associations between exploratory endpoints is described in Table AMBZ.4.2 and AMBZ.4.3.

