4.9 Changes to Protocol-Planned Analyses

There are no changes to the analyses described in the protocol.

5. Sample Size Determination

Approximately 160 participants will be assigned to study intervention. The sample size was determined by considering the precision of the estimated correlation between endpoints. Simulations were performed for both binary and continuous measures where the true correlation varied between CCI . The average half width of the 95% CI for the correlations at Week varied between under considered assumptions for an overall sample size of 160. The average half width of the 95% CI varied between for endpoints during the maintenance period under the assumption that CCI of participants could discontinue early from the study.

Additionally, the proposed sample size of 160 participants is considered sufficient to have power to detect a significant (non-zero) change from baseline in UNRS at Week (primary endpoint).

6. Supporting Documentation

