6.2. Appendix 2: Description of Analyses

 Table AMBZ.6.2.
 Description of Efficacy/Health Outcomes Analyses

Measure	Variable	Analysis Method	Population	Time Point(s)
Urgency NRS	CFB in Urgency NRS Score (Primary Endpoint)	Descriptive summaries, including 95% CI	FAS	Baseline (if applicable), CCI
	UNRS CMI	Descriptive summaries, including 95% CI		
	UNRS Remission	Descriptive summaries, including 95% CI		
	Alternate UNRS Remission	Descriptive summaries, including 95% CI		
CCI	CCI	Descriptive summaries, including 95% CI		
	CCI	Descriptive summaries, including 95% CI		
CCI	CCI	Descriptive summaries, including 95% CI		
	CCI	Descriptive summaries, including 95% CI		
CCI	CCI	Descriptive summaries, including 95% CI		
	CCI	Descriptive summaries, including 95% CI		
Mayo Score and Urgency NRS	Clinical Remission and Urgency NRS	Descriptive summaries, including 95% CI		
	Clinical Response and Urgency NRS COI point Improvement	Descriptive summaries, including 95% CI		
Bowel Urgency			•	
Urgency NRS	UNRS	coefficient with CCI	FAS	Baseline (if applicable), CCI
	CFB UNRS	coefficient with CFB		
	UNRS CMI, UNRS Remission	ANCOVA with CCI and CFB CCI		
CCI	CCI	coefficient with CCI		
	CCI	coefficient with CFB CCI		
QoL Analysis				
CCI	CCI	Descriptive summaries, including 95% CI	FAS	Baseline (if applicable), ccl
	CCI	Descriptive summaries,		

[figure not shown]
Measure	Variable	Analysis Method	Population	Time Point(s)	
		including 95% CI			
		Descriptive summaries, including 95% CI	FAS	Baseline (if applicable), CCI	
		Descriptive summaries,		applicable), cel	
		including 95% CI			
		Descriptive summaries,			
		including 95% CI			
		Descriptive summaries, including 95% CI			
		Descriptive summaries,			
		including 95% CI			
Bowel	UNRS, CCI	CCI			
Urgency Analysis		Score and component subscores			
Allalysis		CCI			
		component scores			
		ccl			
		Pearson + Spearman correlation			
		coefficient with APU			
	CFB UNRS, CFB	CCI			
	CFB	coefficient with CFB CCI and			
	CCI	component scores			
		coefficient with CFB CCI			
		component scores			
		Pearson + Spearman correlation			
		coefficient with CFB CCI			
		coefficient with CFB APU			
		ANCOVA with CC			
		ANCOVA with CC			
Bowel	UNRS CMI, UNRS Remission	ANCOVA with CFB CCI and			
Urgency Analysis	Remission	ANCOVA with Column and			
		components score			
		ANCOVA with CC			
		components score			
		ANCOVA with CFB ccl components score			
		ANCOVA with CFB CC			
		ANCOVA with CC			
		ANCOVA with CFB CC			
		ANCOVA with CO			

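### Does restricting the urgency association analyses to participants still on treatment undermine the correlations the trial was sized for?

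*SAP*

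**What the plan says.** - **The restriction.** SAP Section 4.4.2 opens the topic with "Analysis of association between secondary endpoints is described in" Tables AMBZ.4.2 and AMBZ.4.3, then adds that at two post-baseline weeks (numbers blacked out) "these analyses will be performed among participants with available data that do not discontinue prior to the time point of interest".
- **Its reach.** SAP Section 4.5 sends the exploratory associations to the same two tables ("Analysis of associations between exploratory endpoints is described in") without repeating the restriction. Baseline associations are outside it.
- **The population label.** Table AMBZ.6.2, titled "Description of Efficacy/Health Outcomes Analyses", shows FAS for the urgency blocks (coefficients, ANCOVA, odds ratio and Youden index). SAP Section 3 defines the FAS as everyone assigned and dosed at least once, with the note "Purpose: Used for efficacy and health outcomes analysis".
- **The ED visit.** Protocol Section 1.3 makes it "Required for all participants who discontinue mirikizumab treatment prior to Visit 10". Its column is marked for the row "Diary compliance check, retraining as needed", for the post-baseline tablet questionnaires and for the PGA. Endoscopy is marked at Visits 1, 6 and 10 only.
- **Sizing.** SAP Section 5 bases the 160 participants on the precision of estimated correlations. For the maintenance period it does so "under the assumption that CCI of participants could discontinue early from the study". The half-widths, the true correlations and the dropout percentage are all blacked out.

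**The concern.** Three features together look like a defect. The table names one population and the text uses a smaller one, so a reader of the study report could take correlations among those still on treatment for correlations in everyone treated. The exclusion is not random: Protocol Section 7.1 stops treatment when a participant does poorly and needs higher-dose or prohibited medication, and Section 6.8.2 classes prohibited UC medication as treatment failure. Such exits tend to come from the bad end of both urgency and its paired outcome, and trimming one end of the range usually weakens a correlation. Finally, urgency and questionnaire values taken at the ED visit exist but go unused here.

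At stake is the study's stated purpose, the relationship of urgency to other outcomes. A confidence interval computed on those who remain shows the smaller sample but not the selection.

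**Working it through.** **The plan's own figure.** The inputs behind n = 160 are blacked out, so its half-widths can be neither reproduced nor contradicted. What follows uses assumed correlations and dropout rates.

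**Precision.** The Fisher-z half-width is [tanh(atanh r + s) − tanh(atanh r − s)]/2, with s = 1.96/√(n − 3).

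- r = 0.60, n = 160: s = 1.96/√157 = 0.156 and atanh 0.60 = 0.693. The limits are 0.491 and 0.691, so the half-width is 0.100.
- r = 0.50: 0.117 at n = 160, 0.124 at n = 144 (10% lost) and 0.131 at n = 128 (20% lost).

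Losing 10 to 20% therefore costs 0.007 to 0.014 in half-width.

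**Bias, true r = 0.50, 10% lost.** Removing the top 10% of a standard normal leaves variance v = 1 − 1.282 × 0.195 − 0.195² = 0.712.

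- *Exactly the worst 10% on urgency leave:* r√v / √(1 − r² + r²v) = 0.5 × 0.844 / √(0.75 + 0.25 × 0.712) = 0.438.
- *Leaving has latent correlation 0.5 with urgency:* v becomes 1 − 0.25 × 0.288 = 0.928, giving 0.486 (simulated 0.487).
- *Exactly the worst 10% on urgency plus the paired outcome leave:* the sum's variance falls from 3 to 2.136 and the difference keeps variance 1, so r = (2.136 − 1)/(2.136 + 1) = 0.362 (simulated 0.363).
- *Loss unrelated to outcome:* 0.50.
- *Loss from the middle of the urgency range:* 0.520 (simulated).
- *The most discordant pairs leave:* 0.656 (simulated).

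The shift can be downward, absent or upward.

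**Bias, true r = 0.60, half the loss for lack of efficacy (simulated).**

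| How efficacy-related exits arise | 10% lost | 15% lost |
|---|---|---|
| Worst combined score, no noise | 0.53 | 0.50 |
| Latent correlation 0.7 with combined score | 0.567 | 0.557 |
| Latent correlation 0.5 with combined score | 0.584 | 0.58 |
| Latent correlation 0.5 with urgency alone | 0.590 | 0.588 |

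If all of a 15% loss is for lack of efficacy and selection is strong (worst combined score with noise of 0.5 SD), r falls to about 0.48, a shift of 0.12. With noise of 1 SD it is 0.53, and with 2 SD it is 0.57.

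**Odds ratios.** Write the two-by-two table as a, b (urgency responders) and c, d (non-responders), with odds ratio ad/(bc). If a fraction q of the non-responders is retained regardless of the other endpoint, the ratio is a(qd)/(b(qc)) = ad/(bc), unchanged. Attenuation of the odds ratio needs selection on both endpoints. An ANCOVA contrast is likewise unbiased when selection acts only on its explanatory variable.

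**What carrying ED pairs forward would do.** Suppose 10% leave at random and, because treatment was shorter, both their ED values are worse by δ SD. The pooled correlation is (r + p(1 − p)δ²)/(1 + p(1 − p)δ²), with p = 0.10 and p(1 − p) = 0.09.

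- δ = 1: (0.60 + 0.09)/1.09 = 0.633.
- δ = 1.5: (0.60 + 0.2025)/1.2025 = 0.667.

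The substitute can therefore move r upward by 0.03 to 0.07 where the on-treatment analysis would have no bias.

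**The case for a change.** The strongest reply is that this selection is written into the protocol, that correlations are what the trial was sized to estimate, and that using ED data needs only SAP wording and one more run. Under strong selection the harm is real: with 15% lost and half of that for lack of efficacy, one set of assumptions takes r = 0.60 to 0.52, and the nominal 95% interval then covers the full-population value 73% of the time.

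Part of this stands. The restriction is there, the FAS label does not spell out the subset, and mild attenuation is the most plausible direction if poor responders leave.

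The rest is weaker. Protocol Section 7.2 expects few withdrawals from the study, and Section 7.1 also lists pregnancy, malignancy, infection and hypersensitivity, which need not track urgency. The coverage figure takes the full treated population as the target, which the visible text does not state for these associations; the estimand details and SAP Section 4.1.4 on missing data are not legible. An ED pair cannot include anything that needs endoscopy, so the modified Mayo score, clinical remission and response, and the endoscopic endpoints would stay restricted anyway. ED falls at a variable time with no scheduled efficacy visits after it, and the SoA note requiring at least 4 of 7 diary days names Visits 1, 6 and 10, not ED.

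**Conclusion.** No change to the plan is needed. Table AMBZ.6.2 names the source population across all time points, and Section 4.4.2 then says which of its members contribute at two later weeks. An analyst reading both would run one analysis: FAS participants still in at that week with both measures observed. That estimates a clear quantity, the association among those still on treatment. SAP Section 4.1.1 includes the number of participants in descriptive summaries, and Section 4.2 reports discontinuations with timing and reason, so a reader can judge how many were left out and why.

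The possible bias runs from none, or slightly upward, through 0.01 to 0.03 under moderate selection, to about the 0.10 half-width only when loss is strongly and almost wholly efficacy-driven at about 15%. These sizes assume bivariate normal measures, r near 0.60 and dropout of 10 to 15%; the documents give none of these values. Loss of precision from dropout is already allowed for in the maintenance-period sizing.

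Making ED values the main analysis would trade a possible downward bias for a different estimand and a possible upward one. That is a choice on which statisticians would differ, not a correction. A fuller population label, or a supplementary run with ED pairs for purely patient-reported associations, would be a courtesy to the reader; the planned results do not depend on either.
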